Blood Restriction Training (BFR) is an innovative procedure that involves measuring the Limb Occlusive Pressure, and then setting a tourniquet to a set percentage to restrict blood flow to the exercising body region⁴. It is hypothesized the combination of hypoxia and tension results in metabolic stress and activation of several pathways to increase strength and hypertrophy⁵⁻⁷. Most of the mechanisms are theoretical, but include elevating systemic hormone levels, production of reactive oxygen species (ROS), intramuscular anabolic/anti-catabolic signaling, and increased fast-twitch fiber recruitment.^{4,6-10}. Although the mechanisms are unclear, there is mounting clinical evidence supporting the increase in strength and hypertrophy ^{5,8,9,11-13}. The effect of BFR on pain does show promise when treating knee pathology. BFR has been shown to improve strength, and in some cases pain during exercise as well as or better than conventional therapy in patients with osteoarthritis ¹⁴, and in post-operative patients ^{15,16}. The effect of BFR on pain and function is less clear, and current evidence exists only in knee pathology ¹⁴⁻¹⁸. A 2017 systematic review examining the effect of BFR on musculoskeletal conditions found moderate effect on increasing strength. It appears BFR is not superior to heavy load resistance training, but in the injured population it is not always possible to perform heavy load training ¹⁹.

Regarding safety, there is a very low incidence of side effects with BFR. Wernbom et al⁵ performed a review of the safety reports in 13 BFR specific studies, and the only reported side effects were muscle pain related to the exercise, and some level of endothelial dysfunction related to acute bouts of exercise which resolved within 60 minutes. Nakajima et al²⁰ report on a Japanese survey of KAATSU training (a method very similar to BFR), and report venous thrombosis (0.055%), pulmonary embolism (0.008%), rhabdomyolysis (0.008%). The authors concluded that BFR training is a safe intervention.

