Once randomized, Twenty-two subjects will be placed into a control group, in which standard loading of the wrist and finger extensors using 70% of 1 Rep max (RM), determined using a 1 RM calculator, will be given as well strengthening pronators, supinators and grip strength. The experimental group of 22 will receive blood flow restricted wrist extensor strengthening at 50% limb occlusion using 20% of their 1 RM. To assess 20% of 1 RM of the extensors, a weight will be given to the patient to see how many repetitions can be performed. The weight and number of reps will be entered into a 1 RM calculator so that 20% of the 1 RM can be determined. Strengthening using BFR will occur once per week in clinic, in addition to standard strengthening of supinator, pronators and grip strength. They will also perform the same standardized home exercise program as the control group. All participants will receive the same instruments at baseline and 6th visit. Treatment performed at the three participating clinics will undergo standardized training in the use of BFR strengthening as well as specific study protocol training prior to the onset of the study.

The subjects placed into the control group will receive standard loading of the wrist and finger extensors using 70% of 1 Rep max (RM). The subject will be given the appropriate weight in clinic to be able to do 3 sets of 15. The subject will also strengthen pronators, supinators using a weighted stick to a 7 out of 10 on a rate of perceived exertion (RPE) scale. Grip strength will be addressed using therapeutic putty, resistance determined by the therapist's assessment, having the patient perform 3 sets of 2 min of squeezing the putty. The therapist will have discretion on if cervical spine, thoracic spine or shoulder treatment is warranted, based on standard practice. This treatment will occur for 6 visits in the clinic.

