A combination of physical therapist ([name]), summer research assistant/fellow, and employed certified athletic trainer ([name]) will be assigned to follow through on data collection for the entirety of the follow up period. The research assistant and athletic trainer will have access to patient name, and contact information. They will be authorized to telephone the patient to remind them to fill out their follow up PRTEE and NPRS. If the subject has not filled out their online survey after the 3 standard emails, we will attempt to contact the subject by phone. Each patient may be contacted 3 times, with each phone call one week apart at each follow up time point (3, 6, 12 months). If they have not filled out their survey at that point, we will cease attempts. The subject may ask us not to contact them by phone at any time, and we will not follow up by phone for the remainder of the study.

The final survey will include questions on whether the patient has sought and received other treatment, such as: prescribed medication, surgical intervention, injection therapy, and return to physical therapy.

Serious adverse events will be reported to the IRRB at any time during the active treatment phase of physical therapy, and will be entered into REDCap. This data will also be directly communicated to primary investigators-[name]; [name]; [name], DPT by email and phone. Mild adverse events, such as muscle pain and bruising at the site of BFR cuff will be considered routine and communicated only if it limits ability to treat patient at follow up visits, or leads to alteration in care.

Data Points collected will include:

1. PRTEE and NPRS will be collected at the physical therapy visit at entry, and sixth or last therapy visit. It will be collected electronically by email, with phone call reminders if necessary at 3 months, 6 months, and 12 months from the date of enrollment.
2. Grip Strength (maximum and maximum pain free), and 1 repetition maximum will be collected at entry into study, and 6th / or last visit.

Statistical Analysis

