BFR training has been shown to be safe and can also be applied to persons with various kinds of physical condition including cerebrovascular diseases, orthopedic diseases, obesity, cardiac diseases, neuromuscular diseases, diabetes, hypertension, and respiratory diseases. Nakajima performed a national survey of over 12,000 patients and found that the number of severe side effects is very low. The most frequent side effect is subcutaneous hemorrhage that is transient. Several papers showed that BFR training combined with low-intensity exercise does not cause severe muscle injury, and there is no elevation of creatine phosphokinase (CPK)²⁶ or rhabdomyolysis, as compared with heavy exercises.

Risks include primarily the risk of failure of physical therapy. As we know that therapy has variable responses with this condition, the possibility that the patient does not respond well to either control, or intervention treatment is real.

Medical risks appear very unlikely, with no significant side effects beyond muscle pain reported with BFR in the past.

KAATSU training, which is a Japanese version of blood flow occlusion training, has shown risks of major side effects to be less than 0.1% on a national survey of those using it. These risks included venous thrombo-embolism and rhabdomyolysis.

We believe significant side effects are very unlikely based on published data, and the idea that a trained therapist will be supervising the treatment of our patients.

We cannot envision any significant risk beyond muscle soreness, and possibly skin bruising for patients who have been enrolled in the intervention arm.

Serious Adverse events

Any significant adverse event-such as a venous thrombo-embolism, or significant medical event occurring within 48 hours of treatment will be recorded and reported.

If any significant similar medical event (such as a pulmonary embolism, angina episode, etc.) occurs in patients in any way which indicates a pattern of risk in the intervention group, the investigators will meet to discuss discontinuation of the trial.

Compensation for Injuries

No compensation for injury is planned. Subjects will be informed at the time of consent that any adverse event will be treated and covered as usual by the patient and their health insurance.

Benefits to Subjects

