There is no particular benefit to patients to enrolling in the study. Patients will have to opportunity to receive up to date physical therapy treatment in the control group; and potentially a new and possibly more effective therapy treatment in the intervention group. The primary benefit will be to evaluate a potential new treatment for a condition which is difficult to treat.

Costs to Subject

The cost of participating will be no different than the cost of attending physical therapy generally. Patients will be responsible for whatever costs they would be responsible for when attending therapy. The patients' insurance companies will be billed for standard therapy through the course of treatment.

Compensation to Subject

There will be no compensation for subjects participating in the subjects.

Data/Safety Monitoring

AL, CM, and PT will monitor the results for any report of adverse events. Therapists involved in the project, patients and the blinded assessors will be instructed to contact the investigators with any concern for adverse event. At any time, if there is suspicion of consistent adverse outcome in the intervention group, the 4 investigators mentioned will discuss options, and if no alternative explanation can be found, will discontinue the trial.

AL, CM, and PT will be in contact either in person, by phone, or electronically monthly to discuss the ongoing trial, and will discuss adverse events at point of planned contact.

At this monthly contact, data reporting will be reviewed. We will make efforts in areas of deficiency to contact the enrolling investigator, and ensure that all data is collected. We will also monitor the safety of confidential data.

- a. Monthly Meeting Checklist (once enrollment has begun):
 - i. Number of patients enrolled
 - ii. Barriers to enrolling patients (such as phone enrollment, difficulty getting investigator to first therapy appointment, etc.) with suggested solutions
 - iii. Data entry:
 1. Enrolled patients information is being appropriately entered
 2. Enrolled patients information and consent form is appropriately recorded and protected

3. Any other data concerns
- iv. Safety: Any adverse events or other safety issues
- v. Follow up:
 1. Occurring as planned
 2. Barriers to follow up with suggested solutions

Subject Privacy and Data Confidentiality

Privacy of Participants

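### The stopping discussion is tied to a pattern of events; one serious event in the BFR arm requires no decision before further weekly BFR sessions

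*Combined protocol and SAP*

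**What the plan says.** Two provisions lead to a discussion of stopping.

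- **Serious Adverse events.** "If any significant similar medical event (such as a pulmonary embolism, angina episode, etc".) occurs in a manner "which indicates a pattern of risk in the intervention group, the investigators will meet to discuss discontinuation of the trial".
- **Data/Safety Monitoring.** "At any time, if there is suspicion of consistent adverse outcome in the intervention group", the investigators discuss options, and they end the trial if they find no other explanation.

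Other provisions cover a single event.

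- **Serious Adverse events.** A thrombo-embolism or other significant event within 48 hours of treatment is recorded and reported.
- **Data Collection.** "Serious adverse events will be reported to the IRRB at any time during the active treatment phase of physical therapy". Such events are also entered in REDCap and passed directly to the primary investigators by email and phone. No time limit is given and no action is attached.
- **Data/Safety Monitoring.** Therapists, patients and assessors are told to contact the investigators with any concern. At the monthly contact the investigators "will discuss adverse events at point of planned contact", and safety is a standing checklist item. No decision or record of one is called for.

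On exposure, Therapy Protocols states: "Strengthening using BFR will occur once per week in clinic". The load and rest adjustments in that section deal with missed repetitions, not with adverse events.

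**The concern.** Neither trigger names a number of events, but the words pattern and consistent point to more than one. In an arm of 22 patients receiving a procedure with a very low cited rate of serious harm, a second event of the same kind is unlikely to be seen. A first event may therefore be the only warning the trial gives, and the plan attaches no required decision to it.

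Timing adds to this. BFR is given weekly at three sites, while the scheduled discussion is monthly. Other patients can have further sessions after a serious event without anyone having been obliged to decide that this is acceptable. What is at stake is the safety of patients under treatment and a clear record of the investigators' judgment.

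**Working it through.** The plan states no figure for this rule, so there is none to reproduce. The calculations show how often a first and a second event would be seen.

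**Inputs**
- BFR arm: 22 patients (Therapy Protocols).
- Sessions: 6 per patient, one a week (Timeline of Study), so 22 × 6 = 132.
- Rates: the background paragraph on BFR safety cites a survey of a very similar method, said to "report venous thrombosis (0.055%), pulmonary embolism (0.008%), rhabdomyolysis (0.008"%). Sum: 0.055 + 0.008 + 0.008 = 0.071%.
- Unit: Risks and Side Effects says the method "has shown risks of major side effects to be less than 0.1% on a national survey of those using it", and describes a survey of more than 12,000 patients. That favors a per-person reading but does not settle it, so both readings are shown.

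**Per person (assumption)**
- At least one event in 22: 1 − (1 − 0.00071)^22 = 1.55%.
- After one event, at least one more among the other 21: 1 − (1 − 0.00071)^21 = 1.48%.
- Exact (Clopper-Pearson) 95% interval for 1 in 22: 0.115% to 22.8%. The lower limit is above the cited sum, and just above 0.1%.

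**Per session (assumption)**
- At least one event in 132 sessions: 1 − (1 − 0.00071)^132 = 8.9%.
- After one event, at least one more in the other patients' 21 × 6 = 126 sessions: 1 − (1 − 0.00071)^126 = 8.6%.
- Exact 95% interval for 1 in 132: 0.019% to 4.15%. This includes 0.071%, so one event is a weaker signal.

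**If the true rate is higher than cited.** Take a pattern to mean at least two events (assumption; the plan gives no number) and assume the following per-person rates, with n = 22.

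| Assumed rate | At least 1 | At least 2 | At least 2, given at least 1 |
|---|---|---|---|
| 1% | 19.8% | 2.0% | 10% |
| 2% | 35.9% | 7.1% | 20% |
| 5% | 67.6% | 30.2% | 45% |

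Even at 5%, fewer than half of the trials with a first event would see a second.

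**Sessions before the monthly contact.** For one patient, about 4 of the 6 weekly sessions fit in a month. Across sites, if the 132 sessions are spread evenly over 12 to 24 months (assumption; Potential Limitations of Study mentions a two-year enrollment aim), there are 132/12 = 11 to 132/24 = 5.5 a month. An event at a random time would then be followed by half of these on average, 5.5 to 2.75 sessions, before the next contact. Uneven enrollment could give more.

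**The case against.** The strongest reply is that most of the ground is already covered. Serious events in the treatment phase go directly to the investigators and the IRRB, staff and patients are told to raise any concern, and safety is on every monthly agenda. The investigators may act at any time on suspicion alone, and must stop if they find no other explanation. The meeting rule is also worded in the singular, and its word similar may mean similar in kind to the thrombo-embolism just named, not a repeat of an earlier event. The exclusion criteria remove patients with prior DVT, endothelial dysfunction, peripheral vascular disease, sickle cell disease or trait, and dialysis.

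All of this stands, and it limits the point. A reader might infer that the plan tells the investigators to wait for a second event, or that waiting amounts to not deciding. The documents do not support that: both rules permit action after one event. What is missing is an obligation to decide, and a time by which to do so. A reader might also assume that a single event reaches the investigators at once. Data Collection calls for direct communication but states no deadline.

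It is also fair to say that the signal argument leans on a survey of a related method whose unit is not stated. On the per-person reading the lower limit of 0.115% clears 0.1% only narrowly, and on the per-session reading the interval includes the cited rate. One event would therefore be a reason to look, not proof of excess risk. Nor does the argument extend to angina and similar events: the documents give no rate for them, so one case has not been shown to be a signal.

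**Conclusion.** The point holds in a limited form. The stated triggers for discussing discontinuation look for a pattern or a consistent outcome, which an arm of 22 would rarely show: after a first event, the chance of a second in the other patients is about 1.5% at the cited rates read per person, and 8.6% read per session. A single serious event is communicated and discussed monthly, and the investigators are free to act sooner, but nothing requires a decision before further weekly sessions.

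The practical weight is small, because a first event is itself unlikely at the cited rates (1.6% per person, 8.9% per session). The conclusion about wording rests on the text alone. The sizes rest on the survey rates applying to these patients, on the unit chosen, and on an even spread of sessions. The primary analysis is not affected. This is a cheap improvement to consider, held with low confidence.

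**What to change.** Add to Data/Safety Monitoring, with a cross-reference under Serious Adverse events:

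> One venous thrombosis, pulmonary embolism or rhabdomyolysis in a BFR-arm patient during the treatment phase prompts an investigator review, including alternative cause, before the next BFR session at any site, and the decision to continue, modify or stop is recorded.

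Keep the existing pattern and consistent-outcome rules, and the 48-hour reporting rule, for angina and all other events. The addition is a review trigger, not an automatic stop.

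The cost is a few lines of text and an occasional needless review with a short pause, in about 1.6% of trials at the cited rates (8.9% if per session). On the even-spread assumption, a one-week pause would move 132/104 = 1.3 to 132/52 = 2.5 sessions, which the 12-week window for six visits can generally absorb.
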